8.4 Primary Efficacy Endpoint and Analyses

8.4.1 Primary Efficacy Endpoint

The primary efficacy endpoint is the composite of SRI-4 and steroid dose ≤ 10 mg prednisone equivalent QD at Week 24.

8.4.2 Main Analysis of Primary Efficacy Endpoint(s)

The attributes of the estimand corresponding to the primary efficacy endpoint are summarized in Table 1.

Table 1. Summary of the Estimand Attributes of the Primary Efficacy Endpoint(s)

Attributes of the Estimand					
Estimand Label	Treatment	Endpoint	Population	Handling of Intercurrent Events	Statistical Summary
Primary	
 Elsubrutinib 60 mg QD and upadacitinib 30 mg QD Elsubrutinib 60 mg QD and upadacitinib 15 mg QD Elsubrutinib 60 mg QD and upadacitinib placebo QD Elsubrutinib placebo QD and upadacitinib 30 mg QD Elsubrutinib placebo QD and upadacitinib placebo QD 	Achievement of SRI-4 and steroid dose ≤ 10 mg prednisone equivalent once a day (QD) at Week 24.	FAS	[REDACTED]	Difference in the percentage of subjects achieving SRI-4 and steroid dose ≤ 10 mg prednisone equivalent once a day (QD) between treatment groups.

The primary analysis of the primary endpoint will be conducted on FAS based on randomized treatment groups (each active treatment group vs placebo) using NRI-C for missing data handling. Point estimate and 95% CI using normal approximation will be provided for the response rate for each randomized treatment group. The difference between the treatment groups in the primary efficacy endpoint will be assessed using the Cochran-Mantel-Haenszel (CMH) test and will be stratified by baseline corticosteroid dose above 10 mg prednisone-equivalent (≤ 10 mg or > 10 mg), screening SLEDAI-2K (< 10 or ≥ 10), baseline interferon score (high or low or not applicable), baseline immunosuppressant (azathioprine, tacrolimus, cyclosporine, methotrexate [MTX], mycophenolate) (yes or no). Baseline interferon score for patients in China will be

considered as not applicable. Point estimate, 95% CI and nominal p-value for the treatment comparison will be presented.

ABBV-599 treatment arms will be compared to the corresponding monotherapy treatment arms, in addition to comparison to placebo. All comparisons or analyses are summarized below,

- Each ABBV-599 vs placebo
- Upadacitinib vs placebo
- Elsubrutinib vs placebo
- Each ABBV-599 vs Elsubrutinib
- Each ABBV-599 vs upadacitinib
- Elsubrutinib 60 mg QD and upadacitinib 30 mg QD vs Elsubrutinib 60 mg QD and upadacitinib 15 mg QD

There will be no multiplicity adjustment for the multiple comparisons.

In the event the study is partially terminated, terminated groups will be removed from the comparisons above.

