5.8 Randomization/Drug Assignment

Approximately 325 subjects who meet eligibility criteria will be randomized in a 1:1:1:1:1 ratio to 1 of 5 treatment groups:

- Group 1: Elsubrutinib 60 mg QD and upadacitinib 30 mg QD (n = 65)
- Group 2: Elsubrutinib 60 mg QD and upadacitinib 15 mg QD (n = 65)
- Group 3: Elsubrutinib 60 mg QD and upadacitinib placebo QD (n = 65)
- Group 4: Elsubrutinib placebo QD and upadacitinib 30 mg QD (n = 65)
- Group 5: Elsubrutinib placebo QD and upadacitinib placebo QD (n = 65)

All subjects will be assigned a unique identification number by the IRT at the Screening visit. For subjects who rescreen, the screening number assigned by the IRT at the initial Screening visit should be

used. The IRT will assign a randomization number that will encode the subject's treatment group assignment according to the randomization schedule generated by the statistics department at AbbVie.

Randomization will be stratified based on the following factors:

- Baseline corticosteroid dose above 10 mg prednisone-equivalent (≤ 10 mg or > 10 mg)
- Screening SLEDAI-2K (< 10 or ≥ 10).
- High vs low vs not applicable IFN score (approximately 80% high)
 - This stratification factor does not apply to subjects in China.
- Baseline immunosuppressant (azathioprine, tacrolimus, cyclosporine, MTX, mycophenolate, or leflunomide) (yes/no)

Once approximately 20% of total subjects have been randomized who are IFN signature low, further enrollment of such subjects may be suspended. Please refer to rationale in Section 3.7.

The investigator, study site personnel, and the subject will remain blinded to each subject's treatment throughout the study. AbbVie personnel with direct oversight of the conduct and management of the trial (with the exception of AbbVie Drug Supply Management Team) will remain blinded through Week 24 and will become unblinded only after the primary efficacy analysis at Week 24 is completed. To maintain the blind, the elsubrutinib capsules and matching placebo capsules and upadacitinib tablets and matching placebo tablets provided for the study will be identical in appearance.

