2.3 Treatment Assignment and Blinding

Approximately 325 male and female subjects, 18 to 65 years of age, inclusive, with a diagnosis of moderately to severely active SLE (clinical diagnosis of SLE at least 24 weeks prior to Screening, meeting at least 4 of the 11 revised Criteria for Classification of SLE according to the 1997 Update of the 1982 ACR OR meeting at least 4 of the 2012 Systemic Lupus Erythematosus International Collaborating Clinics [SLICC] classification criteria, including at least 1 clinical criterion and 1 immunologic criterion) despite standard of care therapy will be randomized in a 1:1:1:1:1 ratio of 5 treatment groups, as follows:

- Group 1: Elsubrutinib 60 mg QD and upadacitinib 30 mg QD (n = 65)
- Group 2: Elsubrutinib 60 mg QD and upadacitinib 15 mg QD (n = 65)
- Group 3: Elsubrutinib 60 mg QD and upadacitinib placebo QD (n = 65)

- Group 4: Elsubrutinib placebo QD and upadacitinib 30 mg QD (n = 65)
- Group 5: Elsubrutinib placebo QD and upadacitinib placebo QD (n = 65)

Randomization will be stratified based on the following factors:

- Baseline corticosteroid dose above 10 mg prednisone-equivalent (≤ 10 mg or > 10 mg)
- Screening Systemic Lupus Erythematosus Disease Activity Measure (SLEDAI)-2K (< 10 or ≥ 10)
- High versus low interferon score versus not applicable (approximately 80% high)
 - This stratification factor does not apply to subjects in China.
- Baseline immunosuppressant (azathioprine, tacrolimus, cyclosporine, methotrexate [MTX], mycophenolate) (yes/no)

Once approximately 20% of total subjects have been randomized who are interferon signature low, further screening of such subjects may be suspended. Interferon stratification will be utilized in all participating countries/regions except China due to local constraints.

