* Note: In the event the study is partially terminated, terminated groups will be removed from the comparison.

The binary secondary endpoints will be analyzed using the same approach as that for primary endpoint as specified in Section 8.4.2. Specifically, CMH adjusting for randomization stratification factors will be used to construct the treatment difference, the associated 95% CI and p-value between treatment group comparison. The NRI-C will be the primary approach for missing data handling in the analyses of binary secondary efficacy endpoints.

All continuous endpoints will be evaluated through the change from Baseline. For continuous endpoints with multiple post-Baseline visits, the treatment effect will be assessed through Mixed-effect Model Repeated Measures (MMRM) with treatment, visit

and treatment-by-visit interaction, randomization stratification factors, and the continuous fixed covariate of baseline measurement. An unstructured variance covariance matrix will be used. For continuous endpoints with a single post-baseline visit, the treatment effect may be assessed through analysis of covariance (ANCOVA) with baseline value, treatment, and randomization stratification factors as covariates. In addition, the descriptive statistics for continuous variables will be provided including sample size, mean, standard deviation, median, minimum and maximum.

For the count endpoint (e.g., number of flares by SLENAI SFI), negative binomial regression model will be used to assess treatment effect with treatment, and randomization stratification factors as covariates.

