8.7 Efficacy Subgroup Analyses

To evaluate the consistency of the efficacy over demographic and other baseline characteristics, subgroup analysis will be performed for the primary endpoint for the subgroups listed in Table 3 below. If any of the resulting subgroups except for age, sex and race has fewer than 5% of the Analysis Population, the subgroup analyses for that category will not be presented.

Point estimate and 95% CI for each treatment group as well as point estimate and 95% CI for treatment differences between treatment groups will be presented using the same analysis method as in the primary analysis. P-value for treatment and subgroup factor interaction using Breslow-Day test will also be provided. In addition:

- A logistic regression with treatment group, subgroup, randomization stratification factors, and treatment by subgroup interaction as factors will be performed to evaluate the significance of the interaction between subgroup and treatment group.
- A stepwise logistic regression with treatment group, all subgroup factors, randomization stratification factors will be performed to evaluate potential important subgroup factor(s).

Table 3. Subgroups

Subgroup Factor	Categories
Age at screening	18 – < 40 years old 40 – < 65 years old ≥ 65 years old
Sex	Male Female
BMI	< 25 ≥ 25
Race	White Black Asian Other
Baseline corticosteroid dose	≤ 10 mg > 10 mg
Screening SLEDAI-2K	< 10 ≥ 10
Baseline immunosuppressant	Yes No
Baseline interferon score	High Low NA
Region	North America/South America, Europe, Asia

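### SAP 8.7 carries the normal-approximation 95% interval for single-arm response rates into subgroups that may hold only a few subjects per arm, where its coverage can fall well below 95%; a minor correction to descriptive output.

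*SAP*

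**What the plan says.** SAP 8.4.2 fixes the method for the response rate in a single arm: "Point estimate and 95% CI using normal approximation will be provided for the response rate for each randomized treatment group". In the full analysis set that means about 65 subjects per arm.

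SAP 8.7 plans subgroup results for the primary endpoint. It asks for "Point estimate and 95% CI for each treatment group as well as point estimate and 95% CI for treatment differences between treatment groups", and the same sentence goes on to say that these "will be presented using the same analysis method as in the primary analysis". Read naturally, that covers both the per-arm intervals and the difference intervals. The only size limit is a suppression rule: "If any of the resulting subgroups except for age, sex and race has fewer than 5% of the Analysis Population", that category is not shown. Age, sex and race are exempt from it.

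Interferon score is one of the subgroup factors in SAP Table 3. Its low category has a planned size, because SAP 2.3 allows screening of such subjects to be suspended "Once approximately 20% of total subjects have been randomized who are interferon signature low"; Protocol 5.8 has a matching rule for enrolment.

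Neither document gives an exact, score or other small-sample interval as a fallback.

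**The concern.** The normal-approximation (Wald) interval is the observed rate plus or minus 1.96 estimated standard errors. With few subjects the estimated standard error is itself unreliable. It is exactly zero when no subject responds or when all do, so an arm with 0 of 3 responders would print as 0% (0%, 0%). The table would then look most certain where the data are thinnest.

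SAP 8.7 exists to show whether efficacy is consistent across subgroups. In a descriptive table, the per-arm interval is the reader's only statement of how well each arm's rate is known. If it is labelled 95% and covers far less, small arms may be over-read.

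**Working it through.** **Inputs.** Five arms of 65, total 325 (Protocol 7.7, SAP 2.4). Assumed placebo rate 25% and difference 20 to 25 points, so active rates of 45% to 50% (same sections). Display cutoff 5% (SAP 8.7). Interferon-low share about 20% (Protocol 5.8, SAP 2.3).

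**The plan's own figure first.** Two-sided chi-squared test, alpha 0.10, 65 per arm, pooled variance under the null:

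- 25% vs 45%: (0.20 − 1.645 × √(2 × 0.35 × 0.65/65)) / √((0.25 × 0.75 + 0.45 × 0.55)/65) = 0.76, power 77.7%.
- 25% vs 50%: the same formula gives 1.34, power 91.1%.

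This reproduces the stated 78% to 91%, so the rates and arm sizes are read as the plan intends.

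**Subgroup sizes.** Display cutoff: 0.05 × 325 = 16.25 subjects, and 16.25/5 = 3.25 per arm. Interferon-low: 0.20 × 325 = 65 subjects, 13 per arm. Interferon-high, at about 80%: 0.80 × 65 = 52 per arm. All assume 325 treated subjects and equal arm sizes within the subgroup.

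**Method.** For each n and true rate p, coverage is the sum of the binomial probabilities of those x for which x/n ± 1.96 × √((x/n)(1 − x/n)/n) contains p. The probability of zero width is (1 − p)^n + p^n. No imputation is assumed.

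**n = 3, p = 25%.** The intervals at 0/3 and 3/3 have zero width and miss 25%. Those at 1/3 (−20% to 87%) and 2/3 (13% to 120%) contain it. Coverage = 1 − 0.75³ − 0.25³ = 1 − 0.4219 − 0.0156 = 56.2%. Zero width: 43.8%.

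**n = 13, p = 25%.** The upper limit at 1/13 is 22%, which misses; at 2/13 it is 35%, which covers. The lower limit at 6/13 is 19%, which covers; at 7/13 it is 27%, which misses. Coverage = P(2 ≤ X ≤ 6) = 1 − 0.0238 − 0.1029 − 0.0243 = 84.9%. Zero width: 0.75¹³ + 0.25¹³ = 2.4%.

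| n per arm | True rate | Wald coverage | Zero width | Wilson coverage |
|---|---|---|---|---|
| 3 | 25% | 56.2% | 43.8% | 98.4% |
| 3 | 45% | 74.3% | 25.8% | 100% |
| 3 | 50% | 75.0% | 25.0% | 100% |
| 13 | 25% | 84.9% | 2.4% | 95.2% |
| 13 | 35% | 84.1% | 0.4% | 92.4% |
| 13 | 45% | 95.3% | 0.05% | 95.3% |
| 13 | 50% | 90.8% | 0.02% | 97.8% |
| 65 | 25% | 93.3% | 0% | 95.6% |
| 65 | 45% | 95.4% | 0% | 95.4% |
| 65 | 50% | 95.4% | 0% | 95.4% |

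Coverage does not rise steadily with n: at 25% it is 92.4% for n = 10 but 82.7% for n = 12. In the exempt factors an arm can fall below 3; at n = 2 and 25%, coverage is 37.5% and the zero-width probability is 62.5%. The age category of 65 and over is a likely place for this, since eligibility ends at 65 inclusive and it can hold only subjects aged 65 at screening.

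For comparison, 0/3 gives 0% to 56% by Wilson and 0/13 gives 0% to 23%; Wald gives zero width for both.

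**The case against.** The strongest reply is that nothing rests on these intervals. Subgroup analysis is planned for the primary endpoint only, and consistency will be judged from the treatment differences, the Breslow-Day test and the logistic interaction models. No test, stopping rule or stated dose decision uses a single-arm interval. That stands, and it is why this is minor.

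Four stronger readings are tempting, and the documents do not support them.

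- **That coverage of 56% to 85% is general.** Those figures belong to a true rate of 25%, the assumed rate in one arm of five. At the assumed active rates coverage is better, though still poor at n = 3. Figures for lower rates, such as 10%, would rest on a rate that neither document gives.
- **That subgroups of 3 per arm are planned.** That size is the display cutoff. Apart from interferon score, the documents give no expected distribution for the Table 3 factors.
- **That the interferon group of main interest is compromised.** Protocol 3.7 expects benefit in subjects who express the signature. They are about 52 per arm, where coverage is 93–95% at true rates of 25%, 35%, 45% and 50%. The low group is the one affected, and zero-width intervals are rare there.
- **That the secondary endpoints plainly inherit the problem.** SAP 8.5.2 does say "The binary secondary endpoints will be analyzed using the same approach as that for primary endpoint as specified in Section 8.4.2", but what it then specifies is the CMH treatment difference with its interval and p-value. It does not restate a per-arm interval, and with about 65 per arm the method is adequate at the planning rates anyway.

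Nor is Wilson exact: it covers 91.4% at n = 12 and 25%, and 87.5% at n = 4 and 50%. But it never has zero width and never leaves 0–100%.

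**Conclusion.** The point holds as a minor correction. As written, SAP 8.7 will print per-arm intervals labelled 95% that can cover much less in small subgroups: 56% at 3 per arm and 85% at 13 per arm for a true rate of 25%, and 74–75% and 91–95% for rates of 45–50%. Some will have zero width and some will run outside 0–100%.

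This rests on reading the reference in 8.7 to the primary method as covering the per-arm intervals, on 325 treated subjects with balanced arms within subgroups, and on no imputed values. Imputation for COVID-19 missingness could widen some intervals, but does nothing for an arm with no imputed values.

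A reader might infer that the main result is at risk. It is not. The full-set interval is adequate, and the CMH test, the treatment-difference intervals and the power do not use the single-arm interval.

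**What to change.** In SAP 8.7, specify the Wilson score interval for single-arm response rates; or make the change in 8.4.2 so that it carries through.

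Add a pooling rule for NRI-C:

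- Where values were imputed in an arm, apply the score interval to the pooled rate, with an effective sample size equal to the arm's n divided by the ratio of total to within-imputation variance.
- Where no values were imputed, or the pooled rate is 0% or 100%, use the arm's actual n. With no responders in any imputed dataset both variances are zero, so the ratio is 0/0 and cannot be used.
- Do not pool on the logit scale when any imputed dataset has no responders or all responders, because the logit is then infinite.

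The cost is SAP wording and a programming option. The intervals will be asymmetric, and the pooling rule needs a short specification. Design, data collection, the primary test and the sample size stay as they are. The change does not touch the subgroup treatment-difference intervals, which are a separate matter.

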4 INVESTIGATIONAL PLAN

4.1 Overall Study Design and Plan

This is a multi-center, randomized, double-blind, and placebo-controlled Phase 2 study, with a Week 24 primary endpoint, to investigate the safety and efficacy of elsubrutinib and upadacitinib given alone or in combination (ABBV-599 [elsubrutinib/upadacitinib] combination) in subjects with moderately to severely active SLE. The study will continue through Week 48 to further assess maintenance of efficacy and safety of each treatment beyond 24 weeks.

Approximately 325 male and female subjects, 18 to 65 years of age, inclusive, with a diagnosis of moderately to severely active SLE (clinical diagnosis of SLE at least 24 weeks prior to Screening, meeting at least 4 of the 11 revised Criteria for Classification of SLE according to the 1997 Update of the 1982 American College of Rheumatology [ACR] OR meeting at least 4 of the 2012 Systemic Lupus Erythematosus International Collaborating Clinics [SLICC] classification criteria, including at least 1 clinical criterion and 1 immunologic criterion) despite standard of care therapy will be randomized in a 1:1:1:1:1 ratio of 5 treatment groups, as follows:

- Group 1: Elsubrutinib 60 mg QD and upadacitinib 30 mg QD (n = 65)
- Group 2: Elsubrutinib 60 mg QD and upadacitinib 15 mg QD (n = 65)
- Group 3: Elsubrutinib 60 mg QD and upadacitinib placebo QD (n = 65)
- Group 4: Elsubrutinib placebo QD and upadacitinib 30 mg QD (n = 65)
- Group 5: Elsubrutinib placebo QD and upadacitinib placebo QD (n = 65)

Randomization will be stratified based on the following factors:

- Baseline corticosteroid dose above 10 mg prednisone-equivalent (≤ 10 mg or > 10 mg)
- Screening SLEDAI-2K (< 10 or ≥ 10)
- High vs low vs not applicable IFN score (approximately 80% high) (this stratification factor does not apply to subjects in China)
- Baseline immunosuppressant (azathioprine, tacrolimus, cyclosporine, methotrexate [MTX], mycophenolate, or leflunomide) (yes/no)

[figure not shown]

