7.3 Statistical Analyses for Efficacy

Primary Endpoint Analysis

The primary efficacy endpoint, the achievement of SRI-4 and steroid dose ≤ 10 mg prednisone equivalent QD at Week 24, will be assessed for each active treatment group vs the placebo group. The treatment difference will be evaluated using a Cochran-Mantel-Haenszel (CMH) test stratified by randomization stratification factors. ABBV-599 (elsubrutinib/upadacitinib) combination treatment groups will be compared to placebo and the monotherapy treatment groups. Additional comparisons or analyses will be conducted as appropriate. There will be no multiplicity adjustment for the multiple comparisons.

The Week 24 Primary Analysis will be performed when all subjects have completed the Week 24 assessments or have discontinued the study. The Final Analysis will be performed after all subjects have completed all study assessments including the 30-day follow-up phone call.

Non-Responder Imputation while incorporating Multiple Imputation to handle missing data due to **COVID-19 (NRI-C)** will be applied for primary endpoint analysis. As observed (AO) analysis will be performed as the sensitivity analysis for the primary endpoint.

Secondary and Additional Endpoint Analysis

All secondary and additional efficacy endpoints described in Section 3.3 and Section 3.4 will be analyzed as follows:

Categorical variables will be tabulated by the number and frequency. Between-treatment group comparison will be evaluated in the same way as the primary endpoint analysis.

All continuous endpoints will be evaluated through the change from Baseline. For continuous endpoints with multiple post-Baseline visits, the treatment effect will be assessed through Mixed-effect Model Repeated Measures (MMRM) with treatment, visit and treatment-by-visit interaction, main stratification factors, and the continuous fixed covariate of baseline measurement. An unstructured variance covariance matrix will be used. For continuous endpoints with single post-Baseline visit analysis, the

treatment effect may be assessed through analysis of covariance with baseline value, treatment, and stratification factors as covariates. In addition, the descriptive statistics for continuous variables will be provided including sample size, mean, standard deviation, median, minimum, and maximum.

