- Details on MI method are described below:

MI will be performed using observed data excluding data on or after intercurrent events specified in Section [8.2.2](#). Markov Chain Monte Carlo (MCMC) will be first applied to augment data into monotonic missing pattern, where applicable, and PROC MI will be used to generate 30 datasets using the regression method. If the binary endpoints are derived from the continuous variables, PROC MI will be applied to the continuous variables. The variables to be included in the imputation model are: treatment group, randomization stratification factors (baseline corticosteroid dose above 10 mg prednisone-equivalent (≤ 10 mg or > 10 mg), screening SLEDAI-2K (< 10 or ≥ 10), baseline interferon score (high or low or not applicable), baseline immunosuppressant (yes or no), gender, pooled race (White, Black, Asian, or Other), ethnicity, pooled geographic region (North America/South America,

Europe, or Asian), age, baseline BMI, and if applicable, baseline measurement and post-baseline measurements at each visit up to the end of the analysis period. The random seed for MCMC and the random seed for PROC MI are specified in [Appendix E](#). The imputed post-baseline measurements will be rounded to the same precision as the observed data before the determination of responder status. Prior to applying CMH model, subjects will be characterized as responders or non-responders based on MI imputed values if missing due to Covid-19, otherwise subjects will be considered as non-responder for missing due to other reasons in the NRI-C approach. Using the CMH model adjusted by randomization stratification factors, the endpoints will be analyzed using each of the 30 imputed datasets. SAS PROC MIANALYZE will be used to generate the final inferences of the risk difference using Rubin's rule. The rules of handling intercurrent events, as specified in [Section 8.2.2](#), will be applied before and after applying MI for efficacy assessments.

Mixed-Effect Model Repeated Measurements (MMRM)

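### The SAP drops leflunomide from the baseline immunosuppressant factor that the Protocol uses for randomization, including in the primary CMH test

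*SAP*

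**What the plan says.** The Protocol defines the randomization factor twice, both times with six drugs. Section 4.1 has "Baseline immunosuppressant (azathioprine, tacrolimus, cyclosporine, methotrexate [MTX], mycophenolate, or leflunomide) (yes/no" and Section 5.8 has "Baseline immunosuppressant (azathioprine, tacrolimus, cyclosporine, MTX, mycophenolate, or leflunomide) (yes/no".

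The SAP also gives a drug list twice, both times with five drugs. Section 2.3, which describes how subjects are randomized, has "Baseline immunosuppressant (azathioprine, tacrolimus, cyclosporine, methotrexate [MTX], mycophenolate) (yes/no". Section 8.4.2, which specifies the primary CMH test, has "baseline immunosuppressant (azathioprine, tacrolimus, cyclosporine, methotrexate [MTX], mycophenolate) (yes or no". Neither list is presented as a set of examples.

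Both documents state the rule that the analysis follows the randomization:

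- Protocol 7.3: "The treatment difference will be evaluated using a Cochran-Mantel-Haenszel (CMH) test stratified by randomization stratification factors".
- SAP 8.3, on the NRI-C analysis: "Using the CMH model adjusted by randomization stratification factors, the endpoints will be analyzed using each of the 30 imputed datasets".
- SAP 8.3, on the imputation model: "The variables to be included in the imputation model are: treatment group, randomization stratification factors (baseline corticosteroid dose above 10 mg prednisone-equivalent".
- SAP 8.5.2, on the binary secondary endpoints: "CMH adjusting for randomization stratification factors will be used to construct the treatment difference".

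SAP 8.3 and 8.5.2 give the same rule for the MMRM, and 8.5.2 gives it for the ANCOVA and negative binomial models. The Cox model in SAP 8.6 refers to baseline stratification factors. In its baseline table, SAP 7.1 lists leflunomide among the immunosuppressants.

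**The concern.** The SAP treats the factor list in 8.4.2 and the randomization factors as the same thing. Under the Protocol's definition they differ, and the difference falls on one identifiable group, the leflunomide users.

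The rule in SAP 8.1 for subjects randomized in the wrong stratum does not settle the matter. It sends such subjects to their true stratum, but which stratum is true depends on the definition in dispute. Read together with SAP 2.3, it would move leflunomide users out of the stratum in which they were correctly randomized under Protocol 5.8.

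What is at stake is pre-specification. Each comparison in SAP 8.4.2 has two defensible primary estimates and p-values, and the text does not say plainly which is reported. The Table 3 subgroup has the same gap, because it gives yes/no with no drug list. If that subgroup were derived with six drugs as in SAP 7.1 and the stratification factor with five, the logistic models in SAP 8.7 would contain two nearly identical versions of one variable.

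**Working it through.** **Classification.** Protocol 5.1, criterion 10, permits leflunomide as background treatment and allows only one additional immunosuppressant. A compliant leflunomide user therefore takes no other listed drug that would keep the factor at yes. Every such subject is a yes with six drugs and a no with five.

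**The plan's power figure.** Inputs from Protocol 7.7: 65 per arm, placebo rate 25%, difference 20 or 25 points, two-sided alpha 0.10. For the pooled chi-squared test without continuity correction,

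power = Φ{[d − 1.645 × √(2p̄(1 − p̄)/n)] / √([p₁(1 − p₁) + p₂(1 − p₂)]/n)}.

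- 25% vs 45%: p̄ = 0.35, pooled SE = √(0.455/65) = 0.0837, unpooled SE = √(0.435/65) = 0.0818. Power = Φ(0.762) = 77.7%.
- 25% vs 50%: p̄ = 0.375, pooled SE = √(0.46875/65) = 0.0849, unpooled SE = √(0.4375/65) = 0.0820. Power = Φ(1.345) = 91.1%.

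This agrees with the stated 78% to 91%. The calculation is unstratified, so the choice of list does not change it.

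**Subjects affected.** The documents do not give the leflunomide share, so I assume 2%, 5% or 10%. One pairwise comparison has 2 × 65 = 130 subjects. The number that changes stratum is 0.02 × 130 = 2.6, 0.05 × 130 = 6.5 or 0.10 × 130 = 13. The four factors form 2 × 2 × 3 × 2 = 24 strata, or 130/24 ≈ 5.4 subjects per stratum in a comparison.

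**Simulation.** 6,000 trials per setting, 325 subjects in five arms, permuted blocks of 5 within the 24 strata built on the six-drug list. One active arm is compared with placebo by CMH without continuity correction (reject if chi-squared > 2.706), and the difference is the Mantel-Haenszel risk difference. From the plan: placebo rate 25%, effect 20 points (or 0 for type I error). Assumed: 50% on any listed immunosuppressant, 30% on steroid above 10 mg, 50% with SLEDAI-2K of 10 or more, and interferon score 75/19/6% high/low/not applicable. Immunosuppressant use is either not prognostic or lowers response by 20 points (15% vs 35%). In the table, the first value or pair is for not prognostic and the second for prognostic.

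| Share | Mean absolute shift in the difference, no effect (points) | Same, 20-point effect | 95th percentile of shift, all settings | Power, six vs five drugs (%) |
|---|---|---|---|---|
| 2% | 0.44; 0.53 | 0.48; 0.57 | 1.50 to 1.62 | 76.80 vs 76.80; 78.12 vs 77.72 |
| 5% | 0.76; 0.86 | 0.82; 0.94 | 2.08 to 2.44 | 75.87 vs 75.27; 77.73 vs 76.97 |
| 10% | 1.06; 1.17 | 1.15; 1.28 | 2.79 to 3.28 | 76.60 vs 75.57; 78.73 vs 77.15 |

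- Bias: averaged over trials, the two estimates differ by −0.025 to 0.026 points (SE at most 0.021).
- Type I error: 9.47% to 10.45% with six drugs, 9.22% to 10.77% with five (Monte Carlo SE 0.4 points).
- Different verdicts at alpha 0.1: 1.13% to 3.07% of trials with no effect, 1.73% to 4.65% with a 20-point effect.

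A second simulation (4,000 runs, simpler randomization, a 10-point response difference by immunosuppressant use) gave power of 76.5%, 75.8% and 77.1% with six drugs at shares of 3%, 5% and 10%, against 76.1%, 75.2% and 75.9% with five. Type I error was about 10% to 11% with both lists.

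**The case against.** The strongest objection is that this is a clerical slip with little consequence. At 25% vs 45% the standard error of the difference is 8.2 points, so a mean shift of 0.4 to 1.3 points is about 5% to 16% of one standard error. The largest figures need an assumed 10% leflunomide share, and the largest power gap also needs an assumed 20-point prognostic effect. At a 2% share the power gap is 0.0 to 0.4 points. The p-values are nominal, with up to nine comparisons and no multiplicity control. The governing rule, to stratify as randomized, is already written. On the natural reading of SAP 8.1, a leflunomide user entered correctly under Protocol 5.8 was never wrongly stratified.

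Most of this stands as a statement of size, and I claim nothing larger. It does not remove the contradiction. Section 8.4.2 is the most specific text on the primary test, its list is closed, and SAP 2.3 repeats that list as the randomization factor, so a programmer could follow either version in good faith.

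SAP 11.2.3 sends the interim primary endpoint to Section 8.4, and the documents do not say which list the completed interim analysis used. Knowing that would not change the Week 24 result, so I do not ask for it.

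**Conclusion.** The point holds. The SAP's five-drug list conflicts with the Protocol's randomization factor, with the rule to analyse by the randomization factors, and with the SAP's own baseline table. Neither list makes the CMH test invalid or biased. The single-trial estimate moves by 0.4 to 1.3 points on average, power for a 20-point effect is 0.0 to 1.6 points lower with the five-drug list, and about 1% to 5% of simulated trials change verdict at alpha 0.1. These sizes rest on the assumed leflunomide share, stratum prevalences and prognostic effect. The conflict itself rests on the text alone. The list programmed in the randomization system is not in the documents, so they cannot show which list was used in practice. This should be corrected, but it does not threaten the trial's conclusions.

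**What to change.** 1. Check the randomization system's specification for the drug list it used, and whether that list was the same throughout enrolment.
2. If it is the Protocol 5.8 list, add leflunomide to the factor in SAP 2.3 and 8.4.2. Otherwise, bring both documents into line with the list actually used.
3. State once in the SAP that this definition applies to every stratified or adjusted analysis (CMH, MMRM, ANCOVA, negative binomial, Cox, logistic), the imputation model, the Table 3 subgroup and the SAP 8.1 rule, for both the Week 24 Primary Analysis and the Final Analysis. Do this before the team is unblinded at Week 24.

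The cost is one check of the system specification, one word in two places and one sentence. If the list changed during enrolment, one further line is needed on how the affected subjects are classified. Sample size and stated power do not change.
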